- Waveny LifeCare Nursing Home in New Canaan, CT
 - Point Pleasant Nursing Home, Bradenton, Florida
 - Westminster Winter Park/Baldwin Park Nursing Home

Primary Outcome Variables

The subject's score on using the olfactory device will be compared to the PCR results

(SARS-CoV-2 negative or positive) on COVID19 outpatients. As the smell test has a variable scale (0-5) the ideal cutoff will be determined to maximize these factors:

- Sensitivity
- Specificity
- Accuracy

The score with the olfactory device will also be compared to subjects' response to the question "Do you have a new loss of smell or taste?" (current standard). Repeatability will also be examined in a test-retest score conducted within 24 hours with a second device in which the sequence of the odorants is altered.

Secondary and Exploratory Outcome Variables (if applicable)

We will determine if 'asymptomatic' SARS-CoV-2 positive subjects experience a partial loss of smell (hyposmia) and if so determine the fraction of subjects in which this occurs. Sensitivity, specificity and accuracy will be measured.

Visit Schedule Table (Optional). N.A.

Study Flow Chart (optional). N.A.

Abbreviations

Abbreviation	Explanation
HCW	Health Care Worker
UPSiT	University of Pennsylvania Smell Identification Test
COVID-19- or COVID-19+	Negative for COVID-19 virus (as determined by RT-PCR) or Positive for COVID-19 virus (as determined by RT-PCR)
ICU	Intensive Care Unit
IFRA	International Fragrance Association
CPSIA	Consumer Product Safety Information Act

Glossary of Terms

Glossary	Explanation
Anosmia	Full loss of ability to smell odors
Hyposmia (aka. Microsmia)	Partial loss of ability to smell odors
Normosmia	Normal olfactory function and ability to smell odors (most people)
COVID-19	Disease associated with the SARS-CoV-2 coronavirus

Table of Contents

Synopsis.....	3
Primary Objective	3
Secondary Objectives (if applicable)	3
Study Duration.....	3
Study Design	3
Study Population	3
Number of Participants.....	4
Number of Study Sites	4
Primary Outcome Variables	4
Secondary and Exploratory Outcome Variables (if applicable).....	4
Visit Schedule Table (Optional)	4
Study Flow Chart (optional)	4
Abbreviations	5
Glossary of Terms.....	6
1 Introduction	10
1.1 Introductory Statement.....	10
2 Background.....	11
2.1.1 Device Preclinical Experience	11
2.1.2 Device Clinical Experience	11
2.2 Background/prevalence of research topic	11
3 Rationale/Significance	13
3.1 Problem Statement	13

1.1 Introductory Statement

This document is a protocol to evaluate in a non-therapeutic correlative human research study the performance of a non-invasive olfactory device as an indicator of loss of smell, and an initial indicator of COVID-19 positive subjects. The purpose of this protocol is to ensure that this study is to be conducted according to ICH GCP guidelines, CFR 21 Part 812, applicable government regulations and Institutional research policies and procedures.

2 Background

2.1.1 Device Preclinical Experience

A common assay to detect anosmia (loss of smell) is the use of 'scratch-n-sniff™' type of scent cards, as in the long establish University of Pennsylvania SIT (UPSIT) olfactory test (Doty et al, Laryngoscope, 1984, 94, 176-8). Here microencapsulated non-toxic scents are scratched by the test subject, sniffed and in a discriminatory forced-choice manner the subject chooses the best matching scent choice as part of a multiple choice exam. Typically this is a long format taking 10-15 minutes and is optimized to minimize malingering. There are also shorter format tests. This UPSIT type of test is recognized by the FDA for general anosmia and in the field of use of neurological diseases (e.g. Parkinson's and Alzheimer's Disease). However, the UPSIT test is long, expensive and non-variable, neither of which makes it suitable for widespread or repeated testing. [name] designed and had manufactured a new design of olfactory test card (*u-Smell-it™*) that could be deployed widespread. These 'scratch and sniff'™ type devices are deemed safe by the FDA as they are non-invasive and use non-toxic fragrance. The device card proposed here uses the same fragrance and microencapsulation process as used in the NIH Toolbox® tests for loss of smell. Further the fragrances used in the *u-Smell-it™* test kit are compliant with IFRA and its components do not contain oils derived from nuts, wheat or glutens and do not use any phthalates or their derivatives. These formulations are in widespread use in children's books and cards for over 40 years, as well as other consumer markets. Further, the FDA has approved of use of a 'scratch-n-sniff™' for anosmia. As described below there is now strong mounting evidence for the association of anosmia and COVID-19, albeit largely through patient surveys (see Background 2.2).

2.1.2 Device Clinical Experience

A similar style 'scratch and sniff' assay that use 40 odorants (as a 40 card booklet) was recently shown in a study in Iran to identify smell dysfunction in COVID-19 positive inpatients (Moein et al, Int Forum Allergy Rhinol, 2020; PMID: 32301284). Our quick 4-5 single card odorant '*u-Smell-it*' device uses similar microencapsulated scents that are manufactured in an identical process on a single card. It is optimized for speed, cost, and maximizing signal-to-noise in the analysis, and ease of use. The device is very quick to use, taking <60 seconds and our forced choice test has four to five odor options and a "no scent" option that serves to optimize the signal/noise of the assay in a small fast format, as both points are essential for widespread testing. Thus, there is evidence that quantitative testing has value and the Moein study and numerous reports suggest that acute loss of smell (hyposmia) cannot be reliably self-reported and instead needs a quantitative blinded test, as proposed here.

2.2 Background/prevalence of research topic

There is an urgent need for rapid testing on a massive scale (millions of COVID-19 tests/week) and longitudinal testing of high risk people (e.g. HCWs) to identify

COVID-19 positive people. PCR based testing is the gold-standard, but it is estimated that up to 50-times more tests per week will be needed than is currently achieved. The key hypothesis underlying this clinical trial is that loss of smell (anosmia) may analogous to a 'canary-in-a-coalmine' and serve as an indicator of being infected with the COVID-19 coronavirus.

In support of this hypothesis emerging evidence has come from a number of different countries and includes the following studies (only some are fully peer reviewed):

- Anecdotal evidence suggests loss of smell (and taste) in COVID-19+ patients and may be an early onset factor (1)
- A paper from 12 European hospitals in 6 countries showed that 85% of COVID-19+ people reported loss of smell (anosmia); this paper was based on patient surveys and self-reports of smell loss. (2)
- In an European self-report survey of COVID-19 positive patients 70% reported anosmia and 45% reported fever. Thus anosmia is a better single indicator than fever for COVID-19. (3)
- In contrast, in a Korean a self-report survey of 3,191 COVID-19 positive patients only 15% reported anosmia, with a mean recovery of 7 days (4).
- A US study showed that smell loss was 10x more likely to be from COVID-19 than other causes; this was based on patient surveys and self-reports of smell loss. (5, 6)
- A study in Iran using olfactory testing showed that 58% of COVID-19+ inpatient had anosmia/severe microsmia and 27% had moderate microsmia. 98% of COVID-19+ inpatients had some type of olfactory dysfunction (7).
- A paper showed that loss-of-smell was a good indicator of being positive for COVID-19 if one eliminates loss of smell associated with a stuffy or runny nose. Unlike other viruses such as influenza and the common coronavirus that also present with loss of smell (8), COVID-19+ patients have loss of smell with no sinus blockage. This supports that loss of smell in COVID-19 patient is a different mechanism than in other viral diseases and may be a good diagnostic indicator.
- SARS-CoV-2 entry factors (ACE2 and TMPRSS2) are highly expressed in nasal cavity and localize to multiciliated cells.
- New loss of taste or smell was recently recognized by the CDC (but not yet WHO) to be a symptom associated with COVID-19.

3.1 Problem Statement

A major problem is the loss of olfaction has been identified as a key symptom of COVID-19, yet the degree to which this really occurs is unclear as most reports are potentially biased, not well controlled, and based on surveys. Here we seek to validate this olfactory device and robustly determine its usefulness in terms of sensitivity, specificity, accuracy and repeatability. Of particular relevance to its sensitivity we seek to identify if COVID-19+ asymptomatic individuals in fact have a mild defect in smell, that can only be identified in a sensitive and objective test, as proposed here.

3.2 Purpose of Study/Potential Impact

We posit that most (or even perhaps nearly all) COVID-19+ individuals have a transitory (~7 day) early loss of smell. If this is true and could be robustly and rapidly measured in a device that could be deployed at large scale repeatedly then this could be ultimately used for a massive pre-testing for COVID-19. If this holds true then this olfactory device could outperform PCR tests in the following areas:

Area	PCR	'u-Smell-it' Device
Cost per test	~\$35 (with labor)	<\$1
Time per test	10 min to 5 days	<1 min
Danger to HCW	Considerable for Nasal Swabs (less for saliva)	None; self-performed
Deployment: #/day in USA	~300,000 currently	> ~1-3 million
False Negative Rate	~15-30%	TBD here
False Positive Rate	<5%	TBD here

If the device performs well it ultimately would be broadly deployed as an initial indicator test to identify people likely infected with SARS-CoV-2 that would be confirmed or refuted by secondary PCR screening. It could also serve as a tool to identify local outbreaks of COVID-19.

3.2.1 Potential Risks

This proposed study poses virtually no risks to the test subjects as it is a non-invasive test with materials that have been used clinical extensively. Firstly, these 'scratch-n-sniff'™ style scent cards use the same odorants have been heavily used in FDA approved studies of anosmia and are part of the NIH toolkit® and meet fragrance safety compliance. A very minor risk of a potential adverse reaction to scents may exist for asthmatics and people with scent allergic and thus these people will be excluded. Their condition will be identified by patient self-report. This study will not prescribe any action to the participant so there is no risk of interpretation.

The only other risk is that the test subject if COVID+ could contaminate the answer form with live virus, and this should be treated as a biohazard. To avoid this risk the consent and answer form will be photographed while the subject is in the car through the closed window (they will merely hold it up) but not showing the full face of the subject so as to hide their identity. Only information needed to interpret the results of the study will be transmitted. Using these digital/electronic consent measures eliminates potential contamination of HCW during the reporting due to the COVID-19 virus. As kindly noted in discussions with [name] the YCCI have a new coronavirus guidance allowing informed consent electronically. In the consent document to the participating subject the addition of an electronic consent in

lieu of a printed document is now explicitly discussed and in so signing the subject would opt in for electronic/digital mediated consent.

3.2.2 Potential Benefits

The major benefit to society would be to potentially provide a robust indicator test for COVID-19 that could be rapidly employed at a large scale at an order of magnitude greater daily testing than currently possible - so as to curtail viral transmission and rapidly identify new outbreaks. While the scaling of the device is feasible, the key open question is its performance characteristics, which this study seeks to address. It also seeks to identify if seemingly asymptomatic may have a minor or transitory symptom of loss of smell, that the test would reveal.

4 Study Objectives

4.1 Hypothesis

The major hypothesis is that a quantitative and unbiased smell test will be a useful tool to identify COVID-19 positive individuals.

The study will address what fraction of outpatients truly have a loss-of-smell (including a partial loss) and is expected to outperform the current question that is used to identify COVID-19 related anosmia “Do you have a new loss of smell or taste?” (yes/no) in terms of sensitivity and specificity.

The study will address if high-risk asymptomatic people whom are SARS-CoV-2 positive have a partial (or perhaps transitory) loss of smell.

4.2 Primary Objective

The primary objective of this study is to validate the utility (sensitivity, specificity and accuracy) of a quantitative non-biased olfactory device for the rapid identification of SARS-CoV-2 infected subjects (as identified by PCR). The performance of the device will also be compared to the standard CDC patient query for ‘new loss of smell or taste’.

Secondary Objectives

The secondary objective is to test if SARS-CoV-2 positive ‘asymptomatic’ COVID-19 subjects may actually present with a mild or transitory defect in smell (hyposmia), which is revealed through our quantitative olfactory smell test.

5 Study Design

[figure not shown]
5.1 General Design Description

This is a non-therapeutic correlative trial. Loss of smell in test subjects will be compared to the presence of SARS-CoV-2 coronavirus and statistically measured.

The study will focus on two cohorts: 'drive-thru' outpatients within the Yale New Haven Health System and in Central Louisiana and people at high-risk of being infected with coronavirus (New Canaan and Florida nursing homes) These sites are chosen as they have a significant incidence of COVID-19, they have on-going PCR testing, and they will provide support staff with experts in ENT to implement these studies.

The tests are double blinded as neither the subject or administering staff/doctor will know the results. The COVID-19 outpatients will be randomly recruited with the only preselection being the elimination of pregnant women, those with pre-existing anosmia, head injury, scent allergies, asthma or a self-reported stuffy/runny nose. These conditions will be identified by patient self-report.

The key features of the study design are:

5.1.1 Study Date Range and Duration

There is a pressing need to begin this study as soon as possible due to the US health and economic crisis. We are ready to begin the clinical trial immediately after the IRB is approved as all the material needed for the test is in hand.

Namely, all the initial materials to begin the study are in hand, including the smell device card, bags, and golf pencils. In discussion with CT **[name]** whom represents Fairfield County (Greenwich & North Stamford) Greenwich Hospital (a Yale New Haven Health System affiliate) was identified as a good site for the drive through outpatient testing. Yale New Haven Hospital is also an ideal site given the volume of testing. The Nursing home of Waveny Life Care in New Canaan as an appropriate site for asymptomatic subjects, for they have done widescale PCR screening and they have at least 30 asymptomatic COVID+ people and staff. The President and CEO of Waveny (**[name], MPA/MHA, FACHE**) is eager to begin as soon as possible and will complete PCR tests of all subjects and provide nurses to assist with administration of the test. They also have ~250 untested employees and thus have a young high-risk cohort and would be eager to test asymptomatics. We expect that the initial testing will be done in < 2 weeks (depending on the local incidence rate), with all completed studies taking as little as 3 weeks, with a maximum estimated duration of ~6 weeks. These studies could begin almost immediately after approval from Yale's IRB.

5.1.2 Number of Study Sites

The planned study sites for the drive-up testing would be Greenwich Hospital, Yale-New Haven Hospital and the **Central Louisiana Department of Public Health**. The asymptomatic study would occur at the Florida based nursing homes and Waveny Life Care nursing home in New Canaan (the President and CEO of this center, **[name]**, strongly supports this study and will provide corresponding PCR testing and support staff). These are the principle sites, outside sites would be considered as long as any testing would be confirmed by PCR and meet all conditions prescribed herein.

5.2 Outcome Variables

5.2.1 Primary Outcome Variables

The subject's score on using the olfactory device will be compared to the PCR results (**SARS-CoV-2 negative or positive**) on COVID19 outpatients. As the '*u-Smell it*' test has a variable scale (0-5) the ideal cutoff will be determined to maximize any one (or combination) of these factors:

- Sensitivity

- Specificity
- Accuracy

We will compare the performance of the smell test to the current CDC metric of self-described assessment of smell loss (the de facto standard – e.g. “I have a new loss of smell or taste”) in terms of sensitivity, specificity and accuracy. Repeatability will also be examined in a test-retest score conducted within 24 hours in a random subset of 25 asymptomatic HCW with a second device in which the order of the odorants is altered.

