6.1 Treatment – Device

6.1.1 Intended Use for Device

The intended use of the ‘u-Smell-it’™ olfactory test device is to in a quantitative, fast and repeated manner rapidly determine if an individual has a loss of smell and if so, based on the score and the precision of the device determine the likelihood that s/he is at risk of being positive for SARS-CoV-2. This result would in turn serve as a quantitative indicator to guide judicious action (analogous to how temperature is used to truly identify a fever vs. patient self-identification) – e.g. a follow up PCR test. The comparative gold standard (most used) is the question of if the person believes that s/he has “a new loss of smell or taste”, as currently stipulated by the CDC (whether performed in a written or electronic questionnaire). While there are other smell based test kits they are either very long (10-15 min) and tedious (UPSIT) and will not be suitable for wide-scale rapid testing, or for the rapid 3-item SIT are non-variable, and as such will not be a blinded test, especially for repeated testing. Thus, we will compare the performance of our *u-Smell-it* test to the user-identified stated “new loss of smell/taste” – and anticipate a real unbiased test to greatly outperform a highly subjective assessment. A related underlying hypothesis that we seek to test in this trial is that COVID19+ people perform poorly in self-assessments and grossly underestimate their loss of smell. If this premise is validated AND the performance of the device is statistically high (especially in terms of sensitivity) then one would seek FDA approval under emergency authorization use (EUA). If this eventually clears the FDA then it would be used in wide scale US testing at the state and federal level.

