 - a. [Alternative should there be any issues with the camera or the patient must get out of the car]: The patient will take the completed test packet, place it back in the pouch and under the windshield. The HCW will take the packet and remove the **Consent Form** and **Multiple choice questionnaire form**, check if it is completed (if ask the patient), and place all remaining materials in a biohazard box for destruction. The Consent form and the Questionnaire will be digitalized (scan or photographed) and linked with EPIC so as to be compared to the PCR test results.
4. Information from the uploaded and **Multiple choice questionnaire form** will be entered by a person authorized to access the information into a table that includes:
 - a. Unique identifier
 - b. Gender
 - c. Age band (10 year)
 - d. Y/N to patient self-identified new loss of smell or taste
 - e. Y/N to patient response to "things in the last year smell different"
 - f. Y/N to patient self-identified blocked or stuff nose
 - g. Individual answers on the 5 window smell test
 - h. RT-PCR results for SARS-CoV-2 (+, - or Inconclusive)
 - i. Any other tests for COVID19 (CT or Serological) if given
5. The data will be analyzed in the following fashion:
 - a. Patients that report a blocked or stuffy nose will be excluded from the main analysis (as COVID-19 loss of smell is not due to nasal congestion); but will be analyzed separately to see how this would confound any interpretation.
 - b. Patients that are denoted SARS-CoV-2 "inconclusive" will be excluded from the main analysis; but will be separately analyzed to see if they colocalize with normosmia or anosmia.
 - c. Patients will be split into SARS-CoV-2 positive and negative. As the negative pool is likely to be much larger it will be statistically matched by gender and age profile (potentially with larger bands – e.g. 20 year, depending on the sample size)

- d. The + and - SARS-CoV-2 groups individual performance on the smell test (score 0-5) will be plotted as a histogram. A cutoff will best be chosen to segregate people with normosmia and anosmia (e.g. score = 2 or 3).
- e. False Positives (FP) and False Negatives (FN) will be identified and used to measure the selectivity and sensitivity, respectfully.
- f. Based on the statistical performance (see Table 1) we will determine when we have enough patients to complete the study with a given value of precision.

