6.4.2 Sample Size Considerations

Upon consultation with Yale biostatisticians Profs. [name] and [name], based on our sampling they calculated the following table to shows the precision of sensitivity/specificity measurements for different sample sizes (Table 1). For example, the 95% confidence interval for 90% sensitivity with 100 subjects ranges from 82 to 95% , but if we have 400 subjects, the confidence interval ranges from 87 to 93% (about +/- 3%). Thus the number of participants will be guided by statistical analysis of the data. A minimal estimate is ~100 outpatients that are SARS-Co-V2 positive so as to have good confidence intervals. Here we presume to have at least 100 age/gender matched SARS-Co-V2 negative subjects. If there are 3:1 SARS-Co-V2 negative to SARS-Co-V2 positive then ~400 outpatients (300 +100) will be tested. For the more exploratory testing with asymptomatics we will limit the study to up to 250 HCW. If the results are encouraging with a loss of smell in asymptomatic the sample size could be increased to increase the precision, as done in the outpatient cohort.

Table 1 (replicated from before): Sample Size Calculations (Width of a 95% confidence interval around the proportion).

*Denominator is those that are COVID+ for sensitivity and those that are COVID- for specificity

Sens/Spec	Sample Size for Denominator*						
	100	150	200	250	300	350	400
0.50	0.20	0.17	0.14	0.13	0.12	0.11	0.10
0.60	0.20	0.16	0.14	0.13	0.11	0.11	0.10
0.70	0.19	0.15	0.13	0.12	0.11	0.10	0.09
0.80	0.17	0.13	0.12	0.10	0.09	0.09	0.08
0.90	0.13	0.10	0.09	0.08	0.07	0.07	0.06

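### The 0-5 card and the Yes/No smell question are compared without a common operating point or a definition of outperforming, so a higher card sensitivity may only reflect a lower specificity

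*Combined protocol and SAP*

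**What the plan says.** All references are to the combined protocol and SAP.

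- **Card cutoff.** Section 5.2.1: "the ideal cutoff will be determined to maximize any one (or combination) of these factors", the factors being sensitivity, specificity and accuracy. Section 6.3, step 5d, takes it from the results of the PCR-positive and PCR-negative groups: "individual performance on the smell test (score 0-5) will be plotted as a histogram", and then "A cutoff will best be chosen to segregate people with normosmia and anosmia (e.g. score = 2 or 3". The values 2 and 3 are examples, not a rule.
- **Comparator.** Section 6.3, step 4, records it as "Y/N to patient self-identified new loss of smell or taste". It has a single operating point.
- **Comparison.** Section 5.2.1: "We will compare the performance of the smell test to the current CDC metric of self-described assessment of smell loss", on the same three metrics. Section 4.1 says the card "is expected to outperform the current question that is used to identify COVID-19 related anosmia", and names sensitivity and specificity without saying whether both must be higher.
- **Not given.** Sections 5.2.1, 6.2.1, 6.4.1 and 6.4.3.1 contain no matched operating point, paired test, significance level, margin or success rule for this comparison. AUC is only to be considered, and is not linked to the question.
- **Sample size.** Section 6.4.2 rests on the width of a confidence interval for one proportion: "A minimal estimate is ~100 outpatients that are SARS-Co-V2 positive so as to have good confidence intervals". Nothing there addresses card against question.

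**The concern.** A test with six score levels can be moved along its ROC curve; a Yes/No item cannot. Calling more card scores abnormal always raises sensitivity or leaves it unchanged, and lowers specificity or leaves it unchanged, whatever the card measures. Set against a fixed point one metric at a time, the card's apparent advantage in sensitivity mixes two things: better discrimination and a different choice of cutoff. The plan has no step that separates them.

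The main cause is the unmatched operating point. Choosing the cutoff on the same subjects adds some optimism but is secondary: a cutoff validated in new subjects would still show the sensitivity gain if its specificity were lower than the question's.

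At stake is the study's answer to an expectation stated in section 4.1 and repeated more strongly in section 6.1.1, that an objective test does better than self-report. Both results come from the same people, so ignoring the pairing also wastes precision.

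**Working it through.** **1. The plan's own figure.** Exact (Clopper-Pearson) 95% limits are 82.4% to 95.1% for 90/100 and 86.6% to 92.8% for 360/400. These match the stated 82 to 95% and 87 to 93%. The same method gives 34 of the 35 widths in Table 1; the other is 0.125 against a printed 0.13. The sample-size figures are sound, but they concern one proportion, not this comparison.

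**2. Inputs.** From the documents: score 0-5, a binary question, about 100 PCR-positives, and 100 to 300 PCR-negatives. Assumed, because the documents do not give them:
- card and question each follow a binormal model with AUC 0.90 and correlation 0.5;
- PCR-negative card scores 0 to 5 occur in 1, 2, 5, 12, 30 and 50%;
- question specificity is 80 to 97%;
- the test is a two-sided 5% exact McNemar test on sensitivity.

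**3. Expected values.** The separation is d = √2 × z(0.90) = 1.414 × 1.282 = 1.812. At false-positive rate f, sensitivity = Φ(d − z(1 − f)), for card and question alike. A low score counts as abnormal.

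| Card abnormal if score ≤ | f | Sensitivity | Sens + spec − 1 |
|---|---|---|---|
| 0 | 1% | 30.4% | 0.294 |
| 1 | 3% | 47.3% | 0.443 |
| 2 | 8% | 65.8% | 0.578 |
| 3 | 20% | 83.4% | 0.634 |
| 4 | 50% | 96.5% | 0.465 |

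Maximising sensitivity plus specificity (Youden) therefore tends to pick ≤ 3, whatever the question's specificity is.

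**4. Equal card against question, 100:100, Youden cutoff.** The difference columns are expected values at cutoff ≤ 3; the last column is simulated, with the cutoff chosen afresh in each trial.

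| Question specificity | Question sensitivity | Card − question, sens | Card − question, spec | Trials with card significantly more sensitive |
|---|---|---|---|---|
| 80% | 83.4% | 0.0 | 0 | about 1% |
| 85% | 78.1% | +5.3 | −5 | about 12% |
| 90% | 70.2% | +13.2 | −10 | about 60% |
| 93% | 63.2% | +20.2 | −13 | about 85% |
| 97% | 47.3% | +36.1 | −17 | about 99% |

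The two tests carry the same information in every row. Only the gap in specificity changes.

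**5. Other cutoff rules.** With 100:300 and a cutoff chosen by accuracy, specificity has three times the weight. Cutoff ≤ 2 gives (0.658 + 3 × 0.92)/4 = 0.855 and ≤ 3 gives (0.834 + 3 × 0.80)/4 = 0.809, so a stricter cutoff is preferred. The false finding falls to about 0-5% for question specificity up to 93%, and is 64% at 97%.

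**6. A second model.** Here the card's false-positive rates were 2, 6, 15, 30 and 55%, the correlation 0.3 or 0.7, and question sensitivity 15% to 85% (the self-report range in section 2.2), with question specificity 80 to 95%. If sensitivity alone is maximised, the false finding occurs in 91-100% of trials. Under Youden it ranges from 99-100% (question 40% sensitive, 95% specific), through 39-51% (70%/90%), to 4-7% (85%/80%). With the question at 50%/90% and 100:300, a worse card (AUC 0.73 against 0.82) was still significantly more sensitive in 56% of trials under Youden. When the equal card was cut at the question's own specificity, the rate was 0.7-2.5%.

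**7. Requiring both metrics.** With significance needed on both, false declarations were 0% in every setting of the second model. But in the first model a truly better card (AUC 0.98 against 0.90) was even numerically higher on both in only about 45% and 10% of trials at question specificity 93% and 97%. Adding a significance requirement could only lower these.

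**The case against.** The best defence is that section 4.1 names sensitivity and specificity together. Read as a joint requirement, that closes the trade-off route. It is a fair reading, but the plan does not state it, section 5.2.1 lists the metrics separately, and the joint rule has the power problem shown above.

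Second, the plan states no test or success rule, and reporting all three metrics would make a loss of specificity visible. That is right: the plan is underspecified, and the McNemar test above is an assumption. A reader might infer that the plan would routinely declare a no-better card superior. The documents do not support that: it follows only in part of the assumption range, and only if sensitivity is read alone.

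Third, a reader might take section 6.1.1, "the performance of the device is statistically high (especially in terms of sensitivity", as saying that the comparison is judged on sensitivity. It concerns the device's own performance before an emergency authorisation is sought, and is joined to a separate premise about self-assessment. Likewise, beating the question is not itself the primary objective: section 4.2 says only that the comparison will also be made, and the synopsis objective omits it.

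Fourth, the card is meant as a first screen confirmed by PCR (section 3.2), so giving up specificity may be intended. That can justify a cutoff. It does not justify saying that the card discriminates better than the question.

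Finally, interpolating between two cutoffs describes a rule nobody would apply in practice. True, but it is used here only to put both tests at the same specificity.

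**Conclusion.** The concern holds as a gap in the definition of the comparison. The plan allows a tunable score to be set against a fixed point with no matching, no pairing and no meaning for outperforming. An equally informative card can then appear significantly more sensitive.

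The size runs from about 1% to 99% of trials under a Youden cutoff with equal groups, and from near 0% to 64% with a 3:1 ratio and an accuracy cutoff. It is 91-100% if sensitivity alone is maximised, which section 5.2.1 literally permits although the examples in section 6.3 point to a more moderate cutoff. These figures rest on the assumed question specificity, score distribution, AUC and test, and no single one should be quoted as the error rate of this trial. The direction of the effect rests only on the card being cut at lower specificity than the question.

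This is a change the sponsor should make; it does not invalidate the estimates of the card's own sensitivity and specificity as a design goal.

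**What to change.** In sections 5.2.1 and 6.4.3.1, before data are examined:

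1. Define the comparison as card sensitivity at the question's observed specificity, by linear interpolation between the two adjacent card cutoffs, minus question sensitivity, in the same subjects.
2. Give a 95% confidence interval from a bootstrap that resamples PCR-positives and PCR-negatives separately and repeats the whole calculation each time.
3. State that the card outperforms the question only if the lower limit is above 0.
4. Report the paired differences in sensitivity and in specificity at the chosen cutoff side by side, as description.

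Under the first model with 100:100 subjects (600 trials, 300 resamples each), false claims were 2.8% and 2.5% at question specificity 93% and 97%. A repeat with new random numbers gave 1.3% and 3.5%, in line with the 2.5% expected on one side. Power for the better card (AUC 0.98 against 0.90) was 81% and 56%.

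**Cost.** SAP wording and a short program; the window answers, the Yes/No reply and the PCR result are already recorded. Interpolation on a six-level score is slightly conservative, by about 2-3 points of sensitivity in the simulation, and power is moderate when the question is very specific.
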